- f. **Dose Limiting Criteria:** Subjects who develop any grade 3 or greater toxicity as per NCI CTCAE v. 4 toxicity criteria, Grade 2 or greater autoimmune toxicity with the exception of vitiligo, or Grade 2 or greater hypersensitivity reactions will be treated and referred for additional care as indicated with systemic steroids, topical steroids, epinephrine or Benadryl. These subjects will be removed from the study and will be followed as per protocol defined monitoring and/or until resolution of toxicity.
- g. **Dose Assignment:** Subjects will be treated with vaccine admixed with MONTANIDE™ ISA 51 VG on weeks 1, 2, 3, 7 and 19 in cohorts according to the following dosing diagram:

DLT and the immune-response endpoints are defined in Section 4, “Trial Objectives”. Upon evaluation of all subjects in a cohort (3 or 6 per dose level), the decision whether to escalate, de-escalate or stop will proceed according to the cohort-appropriate schedule shown in **Tables 1, 2, and 3**.

Table 1: Toxicity Decision Rules for Initial Cohort (300 µg Vaccine Dose)

DLTs/ Cohort¹	Action
0/3	Begin accrual to Escalation Cohort
1/3	Expand Initial Cohort to 6 subjects
1/6	Begin accrual to Escalation Cohort
2/6, 3/6, or 4/6	Begin Accrual to De-Escalation Cohort
2/3 or 3/3	Begin Accrual to De-Escalation Cohort

¹ DLT = Dose-Limiting Toxicity

Table 2: Toxicity Decision Rules for Escalation Cohort (500 µg Vaccine Dose)

DLTs/ Cohort¹	Action
0/3 or 1/3	Expand cohort to 6 subjects
1/6	Stop: Declare escalation dose to be MTD ²
2/6, 3/6, or 4/6	Stop: Previous dose level is MTD ²
2/3 or 3/3	Stop: Previous dose level is MTD ²

¹ DLT = Dose-Limiting Toxicity² MTD = Maximum Tolerated Dose**Table 3: Toxicity Decision Rules for De-Escalation Cohort (100 µg Vaccine Dose)**

DLTs/ Cohort¹	Action
0/3 or 1/3	Expand cohort to 6 subjects.
1/6	Stop: De-escalation dose level is the MTD ²
2/6, 3/6, or 4/6	Stop: De-escalation dose level is above MTD ²
2/3 or 3/3	Stop: De-escalation dose level is above MTD ²

¹ DLT = Dose-Limiting Toxicity² MTD = Maximum Tolerated Dose

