If the initial-cohort dose of 300 µg P10s-PADRE is declared to be the MTD and only 3 subjects were enrolled into the initial cohort, then this cohort will be expanded to 6 to assure that 6 subjects are treated at the MTD. The CRA for the trial will assign the subjects to cohorts and communicate the assignments to the research nurse, who will communicate them to the investigator. Only one cohort will be open to enrollment at a time. After the last non-boost dose in each cohort, the study will have a 3-week hold pending the cohort's DLT evaluation. Staggered dosing for the first two patients within each cohort will allow an interval of one week observation for toxicity following the first injection in the previous patient. The research pharmacist will be notified by orders of the registration and cohort dose. Expansion of the cohort to 6, or enrollment to the next cohort, may start once the previous 3 subjects complete their week-9 serology and are evaluated for DLT. Subjects who withdraw from the dose-escalation study without a DLT will be replaced. Subjects who withdraw from the dose- de-escalation study without a DLT will be replaced. Subjects who withdraw with a DLT will be considered evaluable for MTD determination.

8. Risks and Toxicities To Be Monitored

a. Potential Toxicities, Risks and Precautions:

Procedure	Risks	Measures to Minimize Risks
Complete history and physical exam, including blood chemistries	Identification of previously unknown condition	Qualified health care provider to evaluate potential subject Research records are kept in a locked area accessible only by study personnel.

Procedure	Risks	Measures to Minimize Risks

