Subjects will receive up to 5 planned vaccine doses unless they withdraw from the study or develop a dose limiting event as stated above, at which time they will discontinue the injections and be removed from the study. There will be no dose modifications for toxicity. Special attention will be given to toxicities mediated by autoimmune mechanisms, such as colitis, thyroiditis or systemic lupus erythematosus (SLE), as well as to injection-site local reactions or allergic reactions. The NCI CTCAE Version 4.0 will be used for toxicity and SAE reporting. A copy of the CTCAE Version 4.0 can be downloaded from the Cancer Therapy Evaluation Program (CTEP) home page or viewed in **APPENDIX A**. All appropriate treatment areas have access to a copy of the CTCAE Version 4.0.

Any subject may voluntarily revoke consent and withdraw from the study at any time. A subject may be terminated early for the following conditions: (i) non-compliance, (ii) an unrelated intercurrent illness that may affect assessment or place the subject at risk for AEs or require systemic steroids, (iii) deterioration in performance status so as to make participation a hardship for the subject, (iv) for toxicity as determined by the DLT criteria, or (v) for any reason that the investigator feels it is not in the subject's best interest to continue.

- b. Benefits:** As this is the first time Mimotope P10s-PADRE will be administered to humans, there are no clearly defined benefits to subjects of this study. However, this vaccine may potentiate an immune response which could improve median progression-free survival and overall survival of cancer patients.
- c. Injury:** For DOD-funded research, participants can receive medical care at an Army hospital or clinic free of charge. If participants pay out-of-pocket for medical care elsewhere for injuries caused by this research study, they should contact the Principal Investigator. If the issue cannot be resolved, contact the U.S. Army Medical Research and Materiel Command (USAMRMC) Office of the Staff Judge Advocate (legal office) at [contact]/[name]

9. Specimen Handling

Samples will be stored in the UAMS Tissue Procurement Facility, located in room B.018 of the hospital. Cryotubes that contain specimens will be labeled with barcodes. The coded number is linked to patient identification and time of blood draw. Specimens will be stored frozen at -80°C

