a. Sample Size, Study Duration and General Considerations: Because each subject will receive multiple vaccine injections at a constant dose over an extended period of time, the second and third subject of *the same* dose cohort will be enrolled, as available, before the first subject has finished all scheduled injections. However, if two or more subjects are enrolled on the same day, then their injection schedules will be staggered at least one week apart. The decision to escalate or de-escalate the dose, expand the cohort, or terminate the study will be based on assessment for DLTs, which will require 9 weeks per subject. Upon evaluation of all subjects in a cohort (3-6/dose), dose escalation will proceed according to the schedule shown in **Tables 1, 2, and 3**. Except for the fact that they allow for possible de-escalation from the initial dose of 300 μ g, **Tables 1, 2, and 3** constitute the toxicity-based “traditional” design of Storer (43). The time to assess a cohort of 3 for DLTs is anticipated to be 13 weeks based on an accrual rate of 2 eligible Stage IV subjects per month. If no DLTs occur in the initial and final cohorts, then this study will require nine subjects. Subjects who withdraw from the dose-escalation study without a DLT will be replaced. Subjects who withdraw from the dose-de-escalation study without a DLT will be replaced. Subjects who withdraw with a DLT will be considered evaluable for MTD determination. Given the recruitment and immunization/evaluation schedule, we expect this study to be completed in a minimum of 12 and a maximum of 24 months.

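### A subject who stops before Week 9 without a DLT is replaced with no stated toxicity follow-up, and a later DLT has no stated route into Tables 1-3

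*Combined protocol and SAP*

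**What the plan says.** - **Replacement (7.g, repeated in 12.a).** The rule for escalation reads: "Subjects who withdraw from the dose-escalation study without a DLT will be replaced". An identical rule is given for de-escalation. For those who leave after a DLT, the plan says: "Subjects who withdraw with a DLT will be considered evaluable for MTD determination". No minimum exposure, minimum observation time or date for fixing DLT status is attached.
- **Window (7.b, 12.a).** The dose decision rests on "assessment for DLTs, which will require 9 weeks per subject". Injections are given "on weeks 1, 2, 3, 7 and 19 in cohorts", so four of the five fall inside the window.
- **Follow-up after removal (7.f).** Of subjects who met the dose-limiting criteria, the plan says: "These subjects will be removed from the study and will be followed as per protocol defined monitoring and/or until resolution of toxicity". No matching sentence covers anyone else.
- **Other exits (8.a, text after the risk table).** A subject may withdraw consent at any time. Separately, she may be terminated early for non-compliance, intercurrent illness, "deterioration in performance status so as to make participation a hardship for the subject", toxicity under the DLT criteria, or the investigator's judgment. Neither route carries an exit visit or a toxicity check. The text does not say whether subjects terminated early without a DLT are replaced.
- **Long-term follow-up (7.d).** The only procedure listed is serum collection, at six-monthly standard-of-care visits.

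**The concern.** A subject who leaves in Week 4 has not had the 9-week assessment on which the dose decision is meant to rest, yet the replacement rule lets another subject take her place. Under 7.d, full toxicity evaluations fall at Weeks 1, 2, 3, 7 and 9, and the panel with TSH, T4, ANA and liver tests falls at Weeks 3, 7 and 9. Someone who stops between Weeks 4 and 6 was last fully evaluated on the day of her third injection. Her only post-vaccine panel dates from that visit, so it can show little beyond the effect of two injections.

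Section 7.f puts Grade 2 or greater autoimmune toxicity (other than vitiligo) among the dose-limiting criteria. A thyroid or liver abnormality developing in Weeks 5 to 9 may need a blood test to be found, and for this subject none is scheduled.

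This is a first-in-human trial with cohorts of 3 or 6, so one uncounted DLT can change the action. In Table 1 it can turn 1/3 (expand) into 0/3 (escalate), or 2/3 (de-escalate) into 1/3 (expand). Some listed reasons for stopping, such as falling performance status or investigator concern, could be early signs of toxicity.

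**Working it through.** **The plan's own figures.** With no DLTs, the path is 3 subjects at the initial dose and 3 expanded to 6 at the escalation dose: 3 + 6 = 9, as 12.a states. At 2 subjects a month, three subjects span two gaps of about 2 weeks: 2 + 2 + 9 = 13 weeks, also as stated. Both figures rest on subjects completing the 9-week window.

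**Inputs.** From Table 1: escalate on 0/3, or on 1/3 followed by 0/3 (making 1/6). Assumed, because the documents give none of them:
- p: true probability of a DLT by Week 9, independent between subjects.
- h: share of would-be DLT subjects who exit before the DLT.
- d: share of DLT-free subjects who exit before Week 9.

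I also assume that a would-be DLT subject who stops would still have had the DLT from the injections already given.

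**Formulas.** If every exit without a DLT is replaced, the DLT rate among counted subjects is

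q = p(1−h) / [p(1−h) + (1−p)(1−d)]

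and P(escalate, Table 1) = (1−q)³ + 3q(1−q)² × (1−q)³.

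**Complete counting, p = 0.30.** 0.343 + 0.441 × 0.343 = 0.494.

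**Exits only among would-be DLT subjects (d = 0).**

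| p | h | q | P(escalate) |
|---|---|---|---|
| 0.30 | 0 | 0.300 | 0.494 |
| 0.30 | 0.10 | 0.27/0.97 = 0.278 | 0.539 |
| 0.30 | 0.20 | 0.24/0.94 = 0.255 | 0.588 |
| 0.30 | 0.33 | 0.201/0.901 = 0.223 | 0.658 |
| 0.40 | 0 | 0.400 | 0.309 |
| 0.40 | 0.10 | 0.36/0.96 = 0.375 | 0.351 |
| 0.40 | 0.20 | 0.32/0.92 = 0.348 | 0.401 |
| 0.40 | 0.33 | 0.268/0.868 = 0.309 | 0.476 |

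**Exits in both groups, p = 0.30.**
- Equal exit (h = d): the factors cancel, q = 0.30 and P(escalate) stays at 0.494.
- h = 0.10, d = 0.20: q = 0.27/(0.27 + 0.56) = 0.325 and P(escalate) = 0.44. The direction reverses.

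**How often it could arise.** If 5%, 10% or 20% of subjects exit before Week 9, the chance of at least one exit among the first three is 1 − 0.95³ = 14%, 1 − 0.90³ = 27%, or 1 − 0.80³ = 49%.

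**The proposed rule, checked the same way.** Early stoppers are followed to Week 9, DLTs are counted and DLT-free stoppers are replaced, so q = p / [p + (1−p)(1−d)]. With d = 0 this returns p, and P(escalate) is back at 0.494 whatever h is. With 20% of all subjects stopping early at p = 0.30, q = 0.30/(0.30 + 0.56) = 0.349 and P(escalate) = 0.40. Complete counting gives 0.49, as does the current rule under equal exit. The proposed rule therefore leans conservative.

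**The case against.** The strongest reply is that the plan has other safety nets. Section 14 requires data on all registered subjects. Section 16 requires all AEs and SAEs to be recorded and states no cut-off. The medical monitor reviews toxicities regularly (8.a) and meets the team before the next cohort opens (17.a). The stopping rules in 17.b respond to attributed SAEs, related Grade 4 toxicities and deaths not due to cancer. This stands in part: a serious late event could well be noticed. But reporting what comes to light is not a scheduled look, and none of these sections returns a replaced subject's event to the count in Tables 1-3.

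A reader might go further and infer three things that the documents do not support:

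- **That late DLTs can never be counted, or that DLT status is frozen on the day of exit.** The text sets no date for DLT status and does not exclude a later event. It is silent, so the accurate statement is that no route is given.
- **That the rule biases the trial toward escalation.** That needs exit to be more common among subjects heading for a DLT. In stage IV disease, exits unrelated to the vaccine are plausible, and the bias then vanishes or reverses.
- **That subjects terminated for declining performance status are replaced.** The rule speaks of subjects who withdraw, and 8.a treats early termination separately. The exits most plausibly linked to toxicity belong to the group whose replacement is unstated.

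It is also fair to say that follow-up gains little for a subject who withdraws consent for all further contact.

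**Conclusion.** The point holds as a gap in the definition and follow-up of DLT-evaluable subjects, and it should be closed. Following the replacement rule as written can drop a DLT that would have changed a Table 1 action, and no toxicity assessment is scheduled that would find it.

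The size is conditional. At a true DLT rate of 30%, the chance of escalating from the initial cohort is 49% with complete counting. It becomes 54% to 66% if 10% to 33% of would-be DLT subjects leave first and no DLT-free subjects leave, 49% with equal exit, and 44% with 10% exit among would-be DLT subjects against 20% among the rest. The DLT and exit rates are assumptions, and the calculation covers the Table 1 decision only. The case for change is that the plan, as written, would not collect the data needed to tell which of these situations applies.

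**What to change.** In 7.g, 8.a and 12.a, separate stopping injections from leaving assessment, for withdrawn and early-terminated subjects alike:

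1. Any subject with at least one injection who stops before Week 9 keeps the remaining scheduled AE, history/physical and safety-laboratory visits through Week 9, unless she withdraws consent for follow-up.
2. Any DLT in that window counts in her cohort under Tables 1-3.
3. She is replaced only if she is DLT-free at Week 9 or cannot be assessed. State that this applies to early termination as well as withdrawal.
4. Early stoppers are reported by cohort, with reason and Week-9 DLT status.

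**Cost.** No new visit types. On the 7.d schedule, a subject who stops after Week 1 would have up to four toxicity visits (Weeks 2, 3, 7 and 9) plus the blood counts at Weeks 4, 5, 6 and 8. Later stoppers would have fewer. A replacement may start later, by up to 9 − 1 = 8 weeks in that same case. The rule also leans conservative, because DLT-free early stoppers leave the denominator while those with a DLT stay: about 40% rather than 49% chance of escalating in the example above. The protocol should state that lean openly.

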- Toxicity evaluations using the NCI CTCAE (National Cancer Institute Common Terminology Criteria for Adverse Events) Version 4.0. Toxicities to be assessed are the laboratory parameters listed in the study calendar, as well as any sign or symptom found during the history and physical examination not noted at prestudy or on the baseline evaluation. Special attention will be paid to signs and symptoms related to injection reactions, injection site reactions or symptoms or laboratory findings indicating autoimmune toxicities.
- Concomitant medications will be collected from registration to end of treatment.

Week 2

- Administration of the P10s-PADRE/MONTANIDE™ ISA 51 VG vaccine. The vaccine will be administered subcutaneously (SC) by nurses in the Infusion Center at the Cancer Institute.
- Post vaccine administration, the following vital signs will be monitored every 15 (+/- 5 minutes) minutes for one hour: blood pressure, temperature, and pulse.
- Complete medical history and physical examination
- Complete blood count with differential
- Toxicity evaluations using the NCI CTCAE (National Cancer Institute Common Terminology Criteria for Adverse Events) Version 4.0. Toxicities to be assessed are the laboratory parameters listed in the study calendar, as well as any sign or symptom found during the history and physical examination not noted at prestudy or on the baseline evaluation. Special attention will be paid to signs and symptoms related to injection reactions, injection site reactions or symptoms or laboratory findings indicating autoimmune toxicities.
- Concomitant medications will be collected from registration to end of treatment.
- Collection of serum samples used to measure the immune response to the vaccine. If vaccine is given on these days, the study labs will be drawn before the vaccine is administered.

- Study lab samples. Up to 40 mLs of blood will be collected in red and purple tubes for circulating tumor cell evaluation, TACA (tumor associated carbohydrate antigens) assessment, and immune effector assays.

Week 3

- Administration of the study vaccine. The vaccine will be administered subcutaneously (SC) by nurses in the Infusion Center at the Cancer Institute.
- Post vaccine administration, the following vital signs will be monitored every 15 (+/- 5 minutes) minutes for one hour: blood pressure, temperature, and pulse.
- Complete medical history and physical examination
- Complete blood count with differential

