	
hepatic enzymes, hypo-albuminemia with prolonged treatment
 
Neurology: confusion, neuropathies
 
Possible CNS toxicity in those with known metastatic disease to brain
 
Pulmonary: dyspnea (due to fluid retention and capillary leak syndrome), pleuritis
 
Cardiovascular: hypertension, cardiac arrhythmias, atrial fibrillation, pericarditis
 
Pain: headache, arthralgias, bone pain, abdominal pain, chest pain, myalgia
 
Fever, flu-like syndrome (chills, rigors, myalgias), fatigue, headache, abnormal labs including blood urea nitrogen and albumin
	
Thorough review of scans used for disease assessment performed prior to participation in study, including brain imaging.
 
Frequent laboratory tests including CBC with differential, liver function tests, etc.
 
Close and frequent monitoring of subjects by qualified staff.
 
DTH assay to monitor for hypersensitivity reactions
 
Emergency equipment including crash carts, ACLS certified staff and rescue medications such as Benadryl, epinephrine, high dose steroids, etc. will be on-site during administration.
 
The Medical Monitor will review all toxicities on a regular basis and will be available to aid subjects as needed.
 
The study drug may be discontinued.
 
This research is being conducted at an experienced clinical research center in the cancer institute.
 
Reporting and monitoring mechanisms are in place for AEs, SAEs and unanticipated problems.

Collection of blood samples	
Pain, bruising at the injection site and rarely infection
 
Discovery of previously unknown conditions
 
Possible breach of
	
Experienced personnel will perform the phlebotomies using approved techniques.
 
Pressure and dressings will be used to minimize pain, bruising and infection.
 
Research records are kept in a locked area accessible only by study personnel.
 
Subject study numbers will be used for

Procedure	Risks	Measures to Minimize Risks
	confidentiality	identification of samples so that they may be retained for future research and confidentiality is ensured.
Serum pregnancy testing	Discovery of previously unknown conditions Possible breach of confidentiality	Research records are kept in a locked area accessible only by study personnel. Subjects will only be identified by study numbers on all research documents.

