It should be noted that the primary objective of this study is to ensure the safety of the mimotope vaccine. Because of sample size, these studies only provide a qualitative assessment of vaccine immunogenicity. However, our immunization schedule should favor the generation of antibodies (1, 11, 42). A positive TACA-directed immune response will be defined as an anti-TACA serum antibody titer of 1:40 for a baseline pre-vaccination titer of 0 or a \geq 4-fold increase for a baseline titer > 0 (1, 11). A subject will be judged to have had an adequate immune response if they have a positive TACA-directed immune response at any one of the first five indicated time points following vaccine administration on the study calendar (Section 10, Study Lab Weeks 2, 3, 4, 7 and 9). An additional immune-response endpoint will be the DTH response to Mimotope P10s-PADRE. The components of the DTH response, namely, the induration in mm across two diameters, will be tabulated by antigen (the mimotope vs. the two DTH controls) for each subject at the indicated time points on the study calendar. An induration of >5 mm in at least one diameter will be considered a positive DTH response.

b. Data Analysis Plan: Toxicity will be graded according to the NCI CTCAE Version 4.0. All toxicities observed in a study subject will be enumerated and reported in terms of type (organ affected or laboratory determination such as absolute neutrophil count), severity (by NCI Common Toxicity Criteria (CTC) and nadir or maximum values for the laboratory measures), time of onset (i.e. dose number), duration and reversibility or outcome. A toxicity meeting the dose limiting criteria as stated above will be scored as a DLT. The number and proportion of subjects in each dose cohort who suffer a DLT will be reported. The number of DLTs observed will be reported by dose cohort, both overall and also broken down by CTCAE category.

To meet the secondary objective of determining the humoral response against TACAs, the anti-TACA serum titers measured from subjects' blood samples will be collected at pre-study and on weeks 2, 3, 4, 7, and 9. IgM and IgG titers to TACAs will be evaluated by ELISA and

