Any adverse experience that meets reporting guidelines for SAEs must be reported to the CRA for the study in the CCTO within 24 hours of knowledge of the event. The CRA will follow AE reporting plans per institutional policies and applicable regulations. All qualified AEs will be reported to the Investigators, U. S. Army Medical Research and Material Command Human Subjects Research Review Board (HSRRB), FDA, IRB, Medical Monitor, and the UAMS Research Support Center according to this plan.

All AEs and SAEs must be recorded in the appropriate section of the CRF. The report should include, whenever possible, the investigator's written medical judgment as to the relationship of the AE/SAE to study medications(s) (i.e., "probable", "possible" or "unrelated").

Unanticipated problems involving risk to subjects or others, serious adverse events related to participation in the study and all subject deaths should be promptly reported by [contact]), by email ([contact]), or by [contact]) to the U.S. Army Medical Research and Materiel Command, Human Subjects Research Review Board (HSRRB). A complete written report should follow the initial notification. In addition to the methods above, the complete report can be sent to the U.S. Army Medical Research and Materiel Command, ATTN: MCMR-ZB-QH, [name].

17. Monitoring

- a. **Medical Monitor:** The Medical Monitor, Principal Investigator and study staff will meet to review safety data after each cohort has been enrolled and prior to enrollment of the next cohort. Any death will trigger an additional urgent meeting.
- b. **Data Monitor:** UAMS is the IND Sponsor. One (or more) Data Monitor(s) will be appointed by the monitoring division of the UAMS Research Support Center (RSC) to assure that the rights and well-being of human subjects are protected, that the data are accurate, complete and verifiable from source documents and that the trial is conducted in compliance with

currently approved protocol/amendments, with GCP, and with the applicable regulatory requirements set forth in 21 CFR 312.

The Data Monitor(s) will be familiar with the investigational products, the protocol, the informed consent form, any other information provided to the subjects, SOPs, GCP and applicable regulatory requirements.

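### Blood urea nitrogen is named as a MONTANIDE effect in the section on toxicities to be monitored, but is scheduled at 0 of 7 chemistry visits and has no protocol-scheduled baseline

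*Combined protocol and SAP*

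**What the plan says.** Section 8 of the combined protocol and SAP is headed "Risks and Toxicities To Be Monitored". In its table (8.a), the row for MONTANIDE ISA 51 VG names hepatic enzyme elevation and low albumin, and ends with "abnormal labs including blood urea nitrogen and albumin". The measures set against that row include "Frequent laboratory tests including CBC with differential, liver function tests, etc".

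Section 7.d gives the visit-by-visit tests. At each visit with a toxicity evaluation it defines the scope: "Toxicities to be assessed are the laboratory parameters listed in the study calendar, as well as any sign or symptom" found at history and examination and not present before. The Section 10 calendar repeats the laboratory schedule row by row.

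Section 12.b says that "All toxicities observed in a study subject will be enumerated and reported in terms of type", severity, onset by dose number, duration and outcome, with lowest or highest values for laboratory measures. Section 16 adds that "All AEs and SAEs must be recorded in the appropriate section of the CRF", where possible with the investigator's view of the relationship to study medication.

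**The concern.** The plan names three laboratory effects of the adjuvant, and only two of them have scheduled tests. The primary objective is the safety of the P10s-PADRE/MONTANIDE combination, and the 12.b tabulation is how that objective is reported. For an analyte tested only by chance, the maximum value, the time of onset by dose and the reversibility cannot be given reliably.

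Attribution would also be harder. Section 5 admits subjects with stage IV disease, allows chemotherapy, and accepts serum creatinine up to 1.8 mg/dl. A value found abnormal during the trial might have been abnormal before the first dose. Without a scheduled pre-study result, the investigator has no planned comparison on which to base a judgment of relationship. A change without symptoms might not be found at all.

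**Working it through.** The plan gives no figure to reproduce. The check is a count of the visit lists and calendar rows, followed by simple multiplication.

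**1. Chemistry visits.** Section 7.d lists a chemistry panel at pre-study and Weeks 3, 7, 9, 19, 21 and 24: 1 + 6 = 7 visits. Each list has the same 13 entries: SGOT, alkaline phosphatase, LDH, GGT, creatinine, calcium, albumin, amylase, TSH, T4, ANA, bilirubin and PT/PTT. The calendar has the same 13 rows with seven marks each. Column alignment is lost in the extracted calendar, so the second mark could be read under Week 2 or Week 3. Section 7.d places it at Week 3, and the count of seven is unaffected.

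**2. Coverage of the laboratory effects named in the MONTANIDE row.**

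| Named effect | Scheduled test | Visits |
|---|---|---|
| Raised hepatic enzymes | SGOT, alkaline phosphatase, GGT | 7 of 7 |
| Low or abnormal albumin | Albumin | 7 of 7 |
| Abnormal blood urea nitrogen | None | 0 of 7 |

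Creatinine, which the row does not name, is also at 7 of 7. Blood urea nitrogen appears elsewhere only in the abbreviation list.

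**3. Does general wording fill the gap?** The measure quoted from 8.a is open-ended, and the first row of the same table mentions blood chemistries without listing them. Either would permit the test. Neither schedules it, and 7.d refers back to the calendar, which has no such row.

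**4. What the fix would yield.** Each completing subject would have 1 baseline and 6 later values. Three of the later values (Weeks 3, 7 and 9) fall within the 9-week assessment for dose-limiting toxicity (DLT).

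**5. Number of results = subjects × 7.**
- No DLTs: 3 subjects at 300 µg plus 6 at 500 µg = 9, the figure stated in Section 12.a. 9 × 7 = 63.
- Initial cohort expanded (Table 1: "Expand Initial Cohort to 6 subjects") plus one further level expanded to 6: 6 + 6 = 12. 12 × 7 = 84.
- Enrollment goal in the Protocol Summary: 18. 18 × 7 = 126.

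Twelve is not a firm ceiling. Suppose 300 µg passes with 0/3, 500 µg fails after expansion to 6, and 300 µg is then expanded to 6 as the text after Table 3 requires. If that cohort shows 2/6 or 3/6 and Table 1 is applied again, 100 µg would open and could also expand to 6, giving 6 + 6 + 6 = 18. The protocol does not say whether Table 1 is reapplied at that point. All three counts exclude replacements for subjects who withdraw without a DLT.

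**The case against.** The strongest reply is that this is a harmless mismatch between a risk list and a test list. Section 8.a is a table of risks and precautions, and it does not promise one test per entry. The same row lists arrhythmia and pericarditis, and the calendar has no ECG. Renal function is followed by creatinine, which has an entry threshold in Section 5, a pre-study value and six later ones. MONTANIDE is not new: Section 3 reports use in more than 10,000 patients. The documents give no frequency or severity for urea changes, and no endpoint or dose rule depends on the analyte.

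Much of this stands, and it keeps the point small. The first-in-human argument belongs to P10s-PADRE and to the combination, not to the adjuvant alone. Creatinine gives real renal cover. The reply does not explain why, of two analytes named in one phrase, one is measured at every panel and the other never, when adding it needs no extra draw.

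A reader might also infer three stronger things that the documents do not support:
- *That subjects have no baseline value of any kind.* They are under active oncology care and a clinic result may exist. The documents show only that the protocol schedules none.
- *That an abnormal value would go unreported.* If an unscheduled test found one, Section 16 would allow it to be recorded as an adverse event and 12.b would enumerate it. Section 7.d directs assessment to the calendar parameters but does not forbid others.
- *That renal safety is unmonitored.* Creatinine at seven visits rules this out.

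**Conclusion.** The point holds as a gap in scheduled measurement. Blood urea nitrogen is named as an adjuvant effect under a monitoring heading, is scheduled at 0 of 7 chemistry visits, and has no protocol-scheduled baseline. Albumin and creatinine are scheduled at 7 of 7.

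This is a cheap improvement to the safety tabulation and does not show a failure of safety oversight. The expected gain is small, because no criterion in Section 7.f names the analyte and escalation or de-escalation is unlikely to change. The count rests on the 7.d visit lists and the calendar rows, which agree that the analyte is absent. How often the effect occurs cannot be judged from these documents.

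**What to change.** Add blood urea nitrogen to the chemistry list in Section 7.d at pre-study and Weeks 3, 7, 9, 19, 21 and 24, and add a matching row to the Section 10 calendar. Use the pre-study result as the baseline. Let any abnormality enter the 12.b toxicity enumeration with its maximum value. No separate change-from-baseline analysis is needed.

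The cost is one line in each of seven visit lists, one calendar row, and one more analyte on blood already drawn, in the numbers worked out above. Staff would also have occasional incidental abnormal values to review. Rewording 8.a to name creatinine as the renal monitor would tidy the text, but it would leave the analyte unmeasured and without a scheduled baseline, so it does not replace the test.
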